This trial will also be advised by an independent safety monitor. [name], director of continuing medical education at the West Roxbury Veterans Affairs Medical Center, will serve as safety monitor. Recurring meetings between [name], the study PI, and the study research coordinator will be held at least every 6 months to discuss any safety concerns and review all adverse events.

Potential risks

This study should not involve any major risks to screenees or participants and represents minimal risk above usual activities. Both dates and blueberries are widely consumed, readily commercially available, and (as whole fruits) considered healthy food choices. However, there are some potential risks associated with participation in this study, which are as follows:

- Participants may be uncomfortable with certain sensitive questions or questionnaires
- Bruising and a rare chance of local infection from venipuncture to collect blood samples could occur
- Participants may experience transient dizziness during measurement of orthostatic blood pressure
- Application of ABPM and ambulatory electrocardiographic monitoring may disrupt sleep
- There might be loss of confidentiality and privacy

Adverse event surveillance and reporting procedures

An adverse event is defined by the OHRP as “Any untoward or unfavorable medical occurrence in a human subject, including any abnormal sign,... symptoms, or disease, temporally associated with the subject’s participation in the research, whether or not considered related to the subject’s participation in the research.” The National Institute on Aging defines serious adverse events as any adverse event that:

- Results in death,
- Is life-threatening or places the participant at immediate risk of death from the event as it occurred,

- Requires or prolongs hospitalization,
- Causes persistent or significant disability or incapacity,
- Results in congenital anomalies or birth defects,
- Is another condition which investigators judge to represent significant hazards

Surveillance for SAEs and other relevant clinical events that may be associated with study participation will occur at in-person and telephone visits. In addition to the fixed time points, participants may report events in other settings, such as telephone contacts. The PI will review completed forms, will classify the event according to several dimensions (expectedness, relatedness to participation in the trial, and type), and take appropriate action.

Although the duration of the study is relatively short, the older study population increases the likelihood of medical events occurring unrelated to participation in this trial.

All serious adverse events and all unanticipated problems will be reported individually to [name] and the study PI within 7 days of when the research coordinator learned of the event.

In general, all other adverse events will be reported in aggregate form to the study PI and independent safety monitor at the time of regular data reports.

12. Analysis

Experimental design

We will conduct a single-center, randomized, parallel-design trial comparing whole frozen blueberries to an isocaloric serving of dried dates, with single-blind assessment of outcomes among 70 adults aged 70 years and older.

Analysis plan

The trial statistician will conduct all analysis of study data. Working with the PI, the statistician will develop an appropriate analysis plan. Our analyses will be conducted using the intention-to-treat principle, with linear regression models that adjust for baseline values as our primary statistical method.(41) If missing data exist (e.g., due to attrition), linear mixed models that incorporate both baseline and end-of-treatment values will be used. Because randomization in studies of this size can be imperfect, we will also adjust for any baseline characteristics that appear to be uneven (typically at $p < 0.10$). Because of the strong underlying hypotheses and correlated nature of our outcomes, we do not intent to adjust for multiple comparisons, but will treat results that are not corroborated by related outcomes with caution. Methods appropriate for clustered data (e.g., generalized estimating equations) will be used if multiple household members are recruited.

Power and sample size

We estimate power for our continuous endpoints, contrasting end-of-treatment values between arms (using $N=70$). With $\alpha=0.05$ and power=80%, we can detect a 0.68 standardized effect size. This is considered a medium-to-large-sized effect, similar to that tested in many studies of blueberries. With power=50% (i.e., aiming for an exact p -value=0.05), we can detect a 0.48 standardized effect size (medium). Thus, we should detect most moderate-to-large and many medium-sized effects. Thus, we should detect most moderate-to-large and many medium-sized effects.

13. Data Management

Data will be collected from three main sources: 1) data collected by trial staff on case report forms for later entry into REDCap; 2) data entered by participants and/or trial staff directly into REDCap; and 3) data generated by ancillary facilities, such as laboratories, and sent to the trial analysis team directly. REDCap will only be accessible via the secure website and to authorized personnel. REDCap is a secure web application for building and managing online surveys and databases. It is secure behind the BIDMC firewall. All data collected on paper case report forms will be checked before data entry and maintained for later random audits. Any missing data will be marked as such, when possible. Data will be entered as soon as possible after it is collected.

Data confidentiality

All trial staff will be cognizant for strict controls to ensure data integrity. All staff with access to any portion of the study data will receive training on the importance of maintaining participant confidentiality, including appropriate BIDMC HIPAA training and CITI best research practices training. All data collected and stored electronically will be password protected and saved on secure servers. All study-related computers will be located behind BIDMC firewalls and maintain automated virus update mechanisms. Hard copies of data collection forms will be stored in secure areas (locked offices or cabinets). All staff will sign statements attesting to their understanding of and willingness to abide by policies designed to protect the integrity of the study data. General access to the data entry website is password protected with individual usernames and passwords. Data will be backed-up and checked periodically.

14. Timeline

The trial consists of three main phases: planning, implementation (recruitment, intervention, and data collection), and data analysis. Planning for the trial commenced in early 2020 but was put on hold due to COVID-19. Planning for the trial resumed in June 2021. Recruitment will be rolling, commencing in late 2021, and should last approximately 10 months, with randomization beginning within 1-2 months after recruitment. Participants will be followed for 12 weeks after randomization. Remaining time will be devoted to data analysis, presentation, and publication.

Table 5. General Timeline of the Effects of Blueberries in Older Adults Trial.

Activity	Month
Safety officer approval of final MOP	M3
Recruitment efforts and presentations begin	M3-5

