To produce a useful contrast with blueberries, a control food would ideally have several characteristics. These include: 1) low-to-no polyphenol content; 2) sugar content at least as high as blueberries (to enable ready caloric equilibration); 3) availability as a discrete item (to enable easier distribution and simplify instructions on consumption; 4) limited content of other biologically-active factors (e.g., fiber, minerals); 5) appeal to older adults; and 6) long shelf-life. Based on these criteria, we propose to study dates, which have considerable appeal to health-conscious elders, moderate fiber and potassium content (similar to blueberries), long shelf-life (in their dried form), and very low polyphenol content.(33) Conveniently, their high sugar density enables an isocaloric contrast with ~2 dates per day, maximizing ease and adherence among participants.

Significance

Each of our primary and secondary aims has important implications for the health of older adults, can be measured effectively with resources available through the Clinical Research Center (CRC), and has the potential to change in a 12-week period of observation. Moreover, our primary domains have already been linked directly or indirectly to polyphenol intake. This trial takes advantage of a unique partnership between a Harvard-affiliated teaching hospital, Beth Israel Deaconess Medical Center, a Harvard-affiliated geriatric research center, Hebrew SeniorLife, and a congregate living facility, NewBridge on the Charles, to determine a wide range of health effects of whole blueberry intake in older adults in an innovative, cost-efficient, and pragmatic manner.

4. Design

Principal research objective

To conduct a single-center, randomized, parallel-design experimental trial comparing whole frozen blueberries (equivalent to 1 cup of fresh blueberries) to an isocaloric control, with single-blind assessment of outcomes among approximately 46 women and 24 men. Participants must be aged 70 years or older and independent-living residents of NewBridge on the Charles for at least 3 months at randomization. For feasibility, the study uses a pragmatic intervention, comparing blueberries to 2 dried dates daily for 12 weeks. Our specific objectives are to determine the clinical and physiological effects of 12 weeks of daily blueberry consumption primarily on blood pressure, physical function, falls, and cognition in older adults.

5. Study Population and Eligibility

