Participants will be recruited on-site at NewBridge on the Charles by study staff. Because residents live on the campus, we will undertake numerous precautions to educate them regarding the voluntary nature and potential specific importance of our protocol. We will conduct several site-wide introductory presentations about the study to garner interest and awareness. Study staff will be available to answer questions for those interested.

Staff will also provide informational flyers and advertise with posters around the site. Residents will receive a recruitment letter and/or postcard from the study with general information. NBoC has several display monitors throughout campus that are used to share information, activities, and events on campus that the study will use to advertise. In addition, study information will be included in the weekly flyer that is distributed to residents by NBoC. Given the demographic characteristics of individuals at NBoC, we anticipate that women will make up approximately 65% of our study population.

7. Data Collection and Measurements

Data Collection Contact Schedule

Eligibility, baseline, and follow-up data will be collected by phone and at in-person meetings. In-person data collection will be primarily conducted at NBoC in Dedham, MA by the Research Coordinator. However, we will have participants complete blood draws and spot urine collections at the Clinical Research Center in Boston, MA. In some situations and with participant consent, we may have to collect data in other locations (e.g., the participant's apartment on-site), if they cannot get to our clinical location. This would be due to illness or immobility. In general, we will try to be as flexible as possible to meet the needs of our participants. For example, we may divide or bundle data collection, as needed. See Table 2 for proposed data collection items by contact. The primary data collection points for participant-level data are as follows:

Pre-Screen Visit (PSV): A brief medical history questionnaire that asks about conditions noted in the exclusion criteria will be administered by telephone or in person to identify potentially eligible participants quickly and efficiently. Contact information will be recorded for potential participants.

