Cognitive function		X			X
Sleep, quality of life, incontinence, and dietary questionnaires		X			X

Debrief					X
---------	--	--	--	--	---

Measurements

The following sections describe the specific measurements to be collected from participants, in accordance with the above Data Collection Schedule. We have used all of the surveys and questionnaires proposed below in other studies, and all are suitable for older adults. Surveys include the PSQI, (34) the Cogstate Brief Battery, (35) the QUID, (36) the NHANES 2009-10 Dietary Screener Questionnaire (DSQ), (37) and the Health-Related Quality of Life (38). Functional measures include the SPPB and grip strength (39).

For the primary outcomes:

Blood pressure. In this trial, blood pressure will be assessed in several ways. At the BV and the FV, participants will be fitted with and instructed on a 24-hour Ambulatory Blood Pressure Monitor (ABPM). Blood pressure will be continuously monitored and recorded; average wake-time systolic blood pressure will be the primary outcome. Participants will return the ABPM for data upload the following day. At the BV and the FV, participants will undergo seated and supine-to-standing orthostatic blood pressure measurements. A&D Medical ABPMs and software will be used. Omron 907 AOBP machines will be used to measure seated and standing blood pressure.

Physical function. We will assess physical function in various ways. Participants will undergo a grip strength assessment using the average of two measurements in the dominant hand with a Jamar digital handheld dynamometer at the BV and the FV. We will measure functional limitations using the Short Physical Performance Battery (SPPB), an objective assessment developed at the NIA. The SPPB includes timed tests for usual gait speed, balance, and the ability to rise from a chair. A usual-paced 4-meter walk is timed to assess gait speed. For balance, participants are asked to maintain their feet in side-by-side, semi-tandem, and tandem positions for 10 seconds each. Finally, participants are asked to stand up and sit down five times as quickly as possible. Each test is scored from 0 to 4 using cut points from a large population-based study. The final SPPB score, which will serve as the primary functional outcome, is calculated as the sum of the three tests with a range between 0 and 12, with higher scores reflecting better physical performance. Individual components will be secondary outcomes of the trial.

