- Performance monitoring with feedback – tracking enrollment and follow-up (observed/expected, overall and by key subgroups); monitoring missed visits, data completeness, protocol deviations, and data entry errors; distributing feedback through routine trial monitoring reports for the investigators, safety monitor, and IRB as needed. These reports, together with constructive feedback, have an important role in identifying and resolving issues expeditiously.

9. Randomization and Masking

Randomization

Random treatment assignment will be generated via a web-based system available to the research staff. Allocation uses centrally-allocated 1:1 permuted block randomization in blocks of 2 and 4. Eligibility and baseline data will be collected and entered into the database. The system will confirm eligibility and assign the study fruit.

Masking

Because this is a whole foods study, it is not feasible for treatment assignments to be masked to the participants or the research coordinator. Clinicians conducting ABPM and Holter readings and laboratory technicians will be blinded to study groups.

10. Intervention and Control Arms

This trial uses a pragmatic design to maximize generalizability and adherence. Participants randomized to the blueberry arm consume the equivalent of 1 cup of fresh blueberries daily in the form of frozen whole blueberries for 12 weeks. Blueberries are provided in a single-batch from the U.S. Highbush Blueberry Council. All participants have freezers in their apartments to store a supply of blueberries. Surplus storage will be kept in a freezer in the main kitchen for subsequent pick-ups at week 4 and week 8 after randomization.

Those in the control arm are asked to consume no blueberries and to consume an isocaloric portion of dried dates, equivalent to 2 dates daily for 12 weeks. All dates will be pitted and purchased from the same supplier. Dates are an ideal control because they have similar amounts of fiber, potassium, and calories compared to blueberries. The USDA estimates that dates contain approximately 1.6 mg of total polyphenols per 100 gm of edible content (~3 dates). By contrast, blueberries contain approximately 100 mg or more. Therefore, we expect a substantial anthocyanin difference between arms.

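### Sections 4 and 12 claim single-blind outcome assessment without exception, but Section 9 provides it only for ABPM, Holter and laboratory outcomes

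*Protocol*

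**What the plan says.** Section 4 (Design, Principal research objective) describes a randomized parallel-group comparison "with single-blind assessment of outcomes among approximately 46 women and 24 men". It then names four domains as the main objectives: blood pressure, physical function, falls and cognition. Section 12 (Analysis, Experimental design) repeats the description: "with single-blind assessment of outcomes among 70 adults aged 70 years and older". Neither sentence excepts an outcome or refers to another section.

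Section 9 (Randomization and Masking) explains that, because whole foods are being tested, "it is not feasible for treatment assignments to be masked to the participants or the research coordinator". It then lists who is masked: "Clinicians conducting ABPM and Holter readings and laboratory technicians will be blinded to study groups". No other role is listed.

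Section 7 (Data Collection and Measurements) says who takes the measurements: "In-person data collection will be primarily conducted at NBoC in Dedham, MA by the Research Coordinator". Its blood pressure paragraph fixes the ambulatory endpoint: "average wake-time systolic blood pressure will be the primary outcome".

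**The concern.** The phrase in Sections 4 and 12 is attached to the assessment of outcomes as a whole. The main in-person assessor is the person whom Section 9 says cannot be masked. A reader who takes the design from Section 4 or Section 12 alone, for a report or an evidence review, would conclude that physical function, falls and cognition were assessed blind. The protocol does not provide for that.

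At stake is what the trial may claim for those domains, above all for the SPPB and falls. In the ordinary case randomization follows baseline data collection, so knowledge of the assignment can act on the Week 12 measurement and not on the baseline one. Adjustment for the baseline value, which Section 12 plans, would not remove a distortion that enters only at follow-up.

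**Working it through.** No figure in the plan is at issue, so the check sets the sections side by side. The sample size and the stated detectable effects do not depend on masking.

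**Step 1: who is masked.** Section 9 lists ABPM readers, Holter readers and laboratory technicians as masked. It says participants and the research coordinator cannot be.

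**Step 2: how each outcome is obtained (Section 7), and whether a masked role covers it.**

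| Outcome | How obtained | Masked role in Section 9? | Exposure |
|---|---|---|---|
| Wake-time ambulatory systolic pressure | Worn monitor, recording read afterwards | Yes, ABPM reader | Low |
| Cardiac ectopy | Worn Holter, recording read afterwards | Yes, Holter reader | Low |
| Blood and urine measures | Laboratory | Yes, technicians | Low |
| Seated and standing office pressure | Automated: "Omron 907 AOBP machines will be used to measure seated and standing blood pressure" | None named | Limited |
| Grip strength | Digital device: "using the average of two measurements in the dominant hand with a Jamar digital handheld dynamometer" | None named | Limited |
| Cogstate | Laptop test at the visit | None named | Limited |
| SPPB | Three tests timed in person and scored, total 0 to 12 | None named | Greatest |
| Falls | Participant's own record and report, then a staff interview | None named | Greatest |
| Sleep, incontinence, diet and quality-of-life questionnaires | Participant self-report | None named | Self-report by unmasked participants |

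**Step 3: why the SPPB and falls stand out.** The SPPB depends on a person timing gait, balance and chair stands. Falls originate with participants who know their fruit. They keep a daily record, and the weekly questionnaire asks about falls together with intake of the assigned fruit. Masking the staff could not make that first report blind. For office pressure, grip and Cogstate a device produces the reading, so knowledge of the assignment could act mainly through how the session is run.

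**Step 4: count against the Section 4 objective.** Of the four named domains, blood pressure is mixed (ambulatory blind-read, office not covered). Function, falls and cognition have no masked assessor. That is 3 of 4 domains without the stated property.

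**Step 5: does anything else supply masking?** Section 8 provides training, certification and performance monitoring. These serve consistency between measurements; they do not conceal the assignment. In Section 7, *primarily* leaves room for staff other than the coordinator, but no section describes such staff as masked.

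**The case against.** The best defence is that the protocol already discloses the position. Section 9 says who cannot be masked, why, and who is. Sections 4 and 12 are one-phrase summaries and no procedure depends on them. The phrase is true of the endpoint that Section 7 names for blood pressure. All of this stands, and it keeps the point small. It does not make the summaries correct. Nor does it help to say that single-blind means only that one party is masked: the phrase describes outcome assessment, and the main in-person assessor is expressly unmasked.

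A second objection is that the absence of a named masked assessor shows only that masking is unspecified. That is fair for any measure taken by someone other than the coordinator. But an unspecified property cannot be claimed without exception either.

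A reader might also infer more than the document supports:

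- *That the named blood pressure endpoint is compromised.* Wake-time ambulatory systolic pressure is read by blinded clinicians.
- *That the caution rule in Section 12 lets open-label results through once they agree with one another*, such as the SPPB with grip or with its own component tests. That sentence explains the absence of a multiplicity adjustment. It urges caution with uncorroborated results, and does not exempt corroborated ones from caution on other grounds such as open assessment. Nothing in the protocol says that a total's own components count as corroboration. The correlation between a total and its parts would be the same in a fully blinded trial, so it says nothing about masking.
- *That the results will be biased by some stated amount.* The document gives nothing from which to derive one.

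**Conclusion.** The statement in Sections 4 and 12 is wrong as written and should be narrowed. It holds for ambulatory pressure, Holter and laboratory outcomes. It is not provided for office pressure, SPPB, grip, Cogstate, falls or the questionnaires, which leaves three of the four objective domains without it. The practical weight falls on the SPPB and falls.

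This is an inconsistency in the description of the design, not a fault in the choice of endpoint or in Section 9. No bias is quantified and none is claimed. The conclusion assumes that Section 9 lists every masked role; the protocol names no other.

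**What to change.** In Section 4 (Principal research objective) and Section 12 (Experimental design), replace the single-blind phrase with: *blinded reading of ABPM, Holter and laboratory outcomes; all other outcomes are collected without blinding to assignment (see Section 9)*. In reports, describe the function, falls and cognition results as not blind-assessed. If the sponsor does have a masked assessor for one of the other measures, that role should be named in Section 9 and the measure moved to the first part of the phrase.

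The only cost is a weaker stated design claim. Staff, visits, outcomes, their hierarchy and the sample size stay as they are. Section 12's sentence on multiple comparisons needs no change on this account.

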The study population will consist of approximately 70 adults, aged 70 and older, who are independent-living residents of NewBridge on the Charles (NBoC) for at least 3 months at baseline. To enhance the generalizability of this trial, we have a few exclusion criteria. Eligibility will be determined over a series of contacts, including telephone contacts and in-person visits. Table 1 lists eligibility criteria.

Table 1. Eligibility Criteria.

Inclusion Criteria

• Age 70 and older• Independent-living• Resident of NewBridge on the Charles for at least 3 months• Willing to accept randomization to each fruit after tasting both options
Exclusion Criteria

• Myocardial infarction, stroke, or revascularization procedures ≤ 3 months prior to randomization• AHA Class III-IV heart failure• Active titration of blood pressure medication or titration within the last 3 months• Intolerance or allergy to blueberries or dates; allergy to tree nuts, peanuts, soy, or milk products• History of gastric bypass surgery• Planned hospitalization in the ensuing 4 months• Planned vacation lasting >1 week in the ensuing 4 months• Any current cancer treatment• End-stage renal disease• Any organ transplant• Uncontrolled diabetes mellitus with hemoglobin A1c $>9\%$• Inability to provide personal informed consent (e.g., cognitive impairment)• Seated systolic blood pressure > 200 mm Hg at Screening Visit• Investigator concern

6. Recruitment

Field Center

The trial will take place at a single center facility, NewBridge on the Charles, in Dedham, MA. NBoC is a senior living campus operated by Hebrew SeniorLife, a Harvard-affiliated, non-profit care organization. All recruitment and clinical visits, aside from phlebotomy, will be conducted in private space on the NBoC campus. Conducting the study visits at NBoC will be extremely convenient for participants and thus increase retention. Phlebotomy appointments will be conducted at the CRC in Boston, MA. Reimbursement for transportation (i.e. Lyft, Uber) or parking will be provided. All residents have freezers in their kitchens for blueberry storage. There will also be a freezer in the central kitchen dedicated to blueberry storage for later distribution.

Recruitment Strategies

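### Blocks of 2 and 4, disclosed to an unmasked coordinator at a single site, leave the next assignment fairly predictable at the baseline visit; dropping blocks of 2 is a cheap, partial improvement

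*Protocol*

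**What the plan says.** Section 9 (Randomization) gives the scheme: "Allocation uses centrally-allocated 1:1 permuted block randomization in blocks of 2 and 4". It does not give the mix or order of the two sizes, and no stratification factor is named. On access it says "Random treatment assignment will be generated via a web-based system available to the research staff". Under Masking, "it is not feasible for treatment assignments to be masked to the participants or the research coordinator", whereas "Clinicians conducting ABPM and Holter readings and laboratory technicians will be blinded to study groups".

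Section 6 describes one site: "The trial will take place at a single center facility, NewBridge on the Charles, in Dedham, MA". Section 7 covers eligibility, baseline and follow-up data together and says "In-person data collection will be primarily conducted at NBoC in Dedham, MA by the Research Coordinator". Recruitment is by study staff in general: "Participants will be recruited on-site at NewBridge on the Charles by study staff". The exclusion list in Table 1 ends with an open item, "Investigator concern".

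The plan also contains safeguards. Allocation is central, the system confirms eligibility, and REDCap releases the arm only after baseline data collection is complete (Sections 7 and 9). Participants must accept either fruit after tasting both (Table 1). Under Section 10, the second member of a household takes the first member's arm without being randomised.

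**The concern.** Central release protects the list itself. It does not protect against inference, because in a small permuted block the assignments already made constrain those to come. A single unstratified list at one site makes a running tally easy, and a staff member who knows past assignments also handles later participants at baseline.

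Two things could then be affected. The first is who enters which arm: baseline visits can be reordered, and eligibility is confirmed again at that visit, with a discretionary exclusion available. The second is the baseline score on operator-timed tests, chiefly the SPPB, which Section 7 names as the primary functional outcome. Adjusting for baseline values, as Section 12 plans, deals with measured imbalance but not with selection on unmeasured factors.

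Blocks of 2 bring little in return. In an unstratified list of about 70 they are not needed to keep the arms balanced, and the second assignment of every such block is forced.

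**Working it through.** The protocol gives no figure for predictability, so there is none to reproduce.

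**Inputs from the protocol.** Allocation 1:1, block sizes 2 and 4 (Section 9); about 70 participants (Section 12); screening at Week -2 or earlier and a wash-out of 1 to 2 weeks (Section 7); recruitment over about 10 months (Section 14).

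**Assumptions.** The two sizes are equally frequent and in random order, there is one unstratified list, and the observer sees every past assignment. The protocol states none of the three outright.

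**Expected correct guesses.** The rule is to guess the arm that is behind and toss a coin when the arms are level. In a block of size 2m the expected number correct is m + (2^(2m)/C(2m,m) − 1)/2.
- Block of 2: 1 + (4/2 − 1)/2 = 1.5 of 2, or 75%.
- Block of 4: 2 + (16/6 − 1)/2 = 2.833 of 4, or 70.8%.
- Equal numbers of each: (1.5 + 2.833)/6 = 72.2%, about 50 to 51 of 70 against 35 by chance. Any other mix lies between 70.8% and 75%.

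**Where the information sits**, per pair of blocks (6 assignments):
- Arms level: one position in the block of 2, plus 1 + 2/3 in the block of 4. That is 2.667/6 = 44.4%, where the guess is a coin toss.
- Arms unequal: 3.333/6 = 55.6%. Expected correct here is 1 + 2/3 + 1/3 + 1 = 3.0 of 3.333, or 90%. The observer's probability for the favoured arm is never below 0.5 × 1 + 0.5 × 2/3 = 83%, so all of these pass a 75% threshold.
- Certain: if a block of 4 opens with two of the same arm (probability 1/3), its last two assignments are known. That is 2 × (1/3)/6 = 11.1%.

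A simulated Bayesian observer (1,500 sequences of 70) gave 72.1%, 55.5% and 11.1%. If the order of the sizes were fixed and known, the certain share would be (1 + 1 + 1/3)/6 = 38.9%.

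**Comparison with larger blocks, and with intervening allocations** (same simulation):

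| | Blocks 2/4 | Blocks 4/6/8 |
|---|---|---|
| Correct, next assignment | 72% | 68% |
| At least 75% sure | about 55% | about 34 to 35% |
| Certain | 11% | 2% |
| Correct, 1 allocation in between | 56% | 60% |
| Correct, 2 in between | 53% | 57% |
| Correct, 3 in between | 50% | 53% |

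The formula confirms the 68%: (2.833 + 4.1 + 5.329)/18 = 68.1%.

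**Which row applies when.** Seventy participants in about 10 months is 7 a month, or about 1.6 a week. A gap of 1 to 2 weeks between screening and baseline therefore spans about 1.6 to 3.2 allocations on average. The lower rows describe screening; the first three describe the baseline visit.

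**The case against.** The strongest objection is timing. Consent, the main eligibility questions, the taste test and the screening blood pressure come before the wash-out, when other allocations will usually intervene. Prediction is then close to chance, and blocks of 4, 6 and 8 would make it slightly better than blocks of 2 and 4 do. This stands and confines the concern to the baseline visit. The pace is only an average, though, and household second members use no slot, so the gap will vary.

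A reader might infer that assignments are largely known in advance. They are not: about 11% are certain and about 45% are coin tosses.

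A reader might also infer that the main blood pressure result is open to biased measurement. The protocol does not support that. Wake-time systolic pressure comes from an ambulatory device read by blinded clinicians, and office pressure from an automated machine. Cogstate is computer-based, grip uses a digital dynamometer, and laboratory technicians are blinded. SPPB timing and scoring is the main operator-dependent measure.

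Nor does the protocol say that one person enrols everyone and sees every assignment. Study staff recruit, the coordinator's role is described as primary rather than exclusive, and the discretionary exclusion is not given to the coordinator. That one person could keep a full tally is plausible but inferred.

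Finally, larger blocks lower average accuracy by only about 4 points. Withholding the sizes does not lower the 72% at all, because guessing the arm that is behind needs no knowledge of block size; it removes only the certainty. Both points are right, and the remedy is partial.

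**Conclusion.** The point holds as a minor one, a cheap improvement. Nothing in the protocol is contradictory or miscalculated here, and the figures show an opportunity for bias, not that bias occurred. At the baseline visit, about 55% of next assignments can be predicted with at least 75% confidence and about 11% with certainty. What is exposed is selection into arms and baseline SPPB scoring.

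The 72% average hardly depends on the mix of sizes (70.8% to 75%). The 11% does depend on the order being random, and all the figures assume an observer who sees every past assignment. Second household members are a separate matter: their arm is known before their baseline visit under any block scheme.

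**What to change.** Before the first randomisation, load a REDCap allocation table with larger, randomly varying blocks (for example 4, 6 and 8, with none of size 2). Delete the sizes from the protocol and keep them in a document held only by the statistician. Where staffing allows, having someone unaware of past assignments confirm final eligibility and score the baseline SPPB would address the cause more directly than block size can.

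The cost is one new allocation table and a short protocol edit. The largest possible final imbalance rises from 2 to 4 randomised units (for example 37 against 33 of 70), which is negligible for power. Prediction across an intervening allocation becomes slightly easier, about 60% against 56% with one in between. Larger blocks do nothing for the SPPB at follow-up, when the coordinator knows the arm anyway.
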